### **3. Study Design:**

This protocol will recruit approximately 35 Veterans once they enroll in the McGuire VA Medical Center Substance Abuse Treatment Program (SATP) IOP to complete two sessions of questionnaires and neurobehavioral measures, lasting approximately 3 hours in total. Each subject will meet initially with research staff after their SATP intake (conducted as standard of care), but prior to initiating treatment for the first session. Subjects will then meet with research staff again approximately one month later following their completion (or potentially incompletion) of the treatment. Following this meeting, research staff will complete a targeted CPRS medical chart review to collect information on appointment no shows, early termination of services, and results of Urinary Drug Screen (UDS) and Breathalyzer collections, and results of the Beck Depression Scale and Quality of Life Inventory administered during the SATP intake. 90 days following this chart review, a second chart review will occur to collect the same information, if available, for the post-treatment time period, along with information about whether they have re-entered treatment.

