CPRS will also be used to complete a review following the second visit with subjects to collect information on appointment no shows, early termination of services, results of Urinary Drug Screen (UDS) and Breathalyzer collections, and results of the Beck Depression Inventory and Quality of Life Inventory administered during the SATP intake. 90 days following this chart review, a second chart review will occur to collect the same information, if available, for the post-treatment time period, along with information about whether they have re-entered treatment.

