*Quality of Life Inventory (QOLI)* – The QOLI assesses the importance of 16 life domains on a 3-point rating scale, as well as current satisfaction of each domain (6-point scale). The scores are summed to determine quality of life. This is a quick self-report questionnaire that has been normed in a community sample of adults. Higher scores indicate better quality of life. We hypothesize that those with better treatment adherence and less evident impulsivity on neurobehavioral measures will indicate better quality of life (Frisch, Cornell, Villaneuva, & Retzlaff, 1992). This measure takes approximately 10 minutes to complete.

*Beck Depression Inventory-II (BDI-II)* - The BDI-II is a 21-question, multiple-choice self-report questionnaire that is widely used in clinical and research practice for the purposes of measuring reported symptoms of depression. This has been widely established as a reliable and valid measure (Aaron T. Beck, Steer, & Brown, 1996). This measure takes approximately 10 minutes to complete.

The following tasks will be completed via administration by research staff:

*Delis-Kaplan Executive Function System (DKEFS) Tower Test* – The DKEFS Tower Test is a neuropsychological measure examining the executive functioning ability, specifically the ability to plan and sequence behavior. The test consists of two boards with pegs and several beads with different shapes. The test requires the individual to complete a timed-task requiring planning and sequencing in order to move the pegs in an instructed manner. We hypothesize errors on the Tower Test will be significant associated with poorer performance on neurobehavioral measures (as evident by more errors and faster reaction times) and with poorer treatment adherence. Time and errors are considered for scoring. The task requires approximately 10 minutes to complete.

The following laboratory performance measures will be conducted on a desktop computer:

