Day -7 – Day -1	
 
- Contact with potential subjects for recruitment during a face to face meeting when they are in the SATP clinic
 
- Consent and pre-treatment baseline assessment
 
	Brief Addiction Monitor (BAM), Barrett Impulsivity Scale-11 (BIS-11), Posttraumatic Checklist-5 (PCL-5), Beck's Anxiety Inventory
Day 0 – Day 28	
 
- Participants engage in either MFP or TAU treatment during their IOP engagement
 
	N/A
Day 29 – Day 35	
 
- Post-treatment assessment
 
- Chart review: treatment engagement (appointment no shows, early drop out) and Breathalyzer/UDS results, results of Beck Depression Inventory and Quality of Life Inventory.
 
	BIS-11, Delay Discounting Task, Stop-Signal Task, Emotional Go-NoGo task, Quality of Life Inventory
Day 120	
 
- Chart Review: recidivism (treatment re-entry) and Breathalyzer/UDS results
 
	N/A

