#### Data Analysis

The analytic plan includes conducting an independent-group t-test of each of the following continuous dependent variables, or chi-square for categorical dependent variables: 1)

proportion drug-free urines; 2) retention in program (Chi-Square); 3) Quality of life score on the QOLI; 4) Delay discounting constant k; 5) Stop signal reaction time (SSRT) on the stop-signal task; 7) Reaction time in the Emotional Go-NoGo task, 8) errors in the DKEFS Tower Test.

A repeated-measures design will be used to examine the within-subjects effects of the treatments on state depression and quality of life, as well as for a group X treatment interaction effect. Although we do not expect an intervention of this time scale of to alter trait impulsivity, we will also analyze within-subject changes in BIS11 scores as an exploratory analysis. Lastly, a between-group design comparing the MFP group vs. TAU group for substance use primary outcomes of symptomology and neurobehavioral measures for problem solving and impulsivity. Individual differences in PTSD and anxiety measures and other symptomatology will be included as covariates to account for confounding factors in the analyses.

c. Facilities and Resources

The consent procedures and behavioral testing of this protocol will take place in the new second-floor Mental Health services facility at RICVAMC. Written informed consent procedures and clinical interviewing will take place in private interview rooms of this new second-floor RICVAMC wing. Questionnaires and laboratory behavioral tasks will be administered at dedicated research task workstations installed in testing rooms.

d. Staff Qualifications

*[name].* will be the Principal Investigator of this protocol. [name] has a 5/8 VA appointment and a joint (faculty) appointment as Associate Professor of Psychiatry at Virginia Commonwealth University. He has extensive experience in the laboratory testing of impulse control and decision-making in addicted inpatients, outpatients, and at-risk human subjects. He is also known for his successful design and execution of protocols to examine the neurocircuitry of motivation and self-control in addicted and adolescent at-risk populations. He has over 50 peer-reviewed publications and book chapters, 48 of which are available in PUBMED.

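### The MFP versus TAU tests of quality of life and depression do not use the intake score as a covariate, and QOLI has two overlapping tests where one baseline-adjusted ANCOVA would be at least as precise

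*Protocol*

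**What the plan says.** The Data Analysis part of Protocol section 4.b opens with a list of tests: "The analytic plan includes conducting an independent-group t-test of each of the following continuous dependent variables" (chi-square for categorical outcomes). Its third item is "3) Quality of life score on the QOLI". The list does not name the groups being compared.

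The next paragraph adds: "A repeated-measures design will be used to examine the within-subjects effects of the treatments on state depression and quality of life", together with a group interaction. BIS-11 change is analysed within subjects and labelled exploratory. A closing sentence plans an MFP versus TAU comparison of substance use outcomes and of neurobehavioral measures. PTSD, anxiety and unspecified other symptoms are to be covariates. No sentence names an outcome's own pre-treatment value as one.

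Pre-treatment values exist:
- **QOLI and BDI.** The chart review in section 4.a collects "results of the Beck Depression Inventory and Quality of Life Inventory administered during the SATP intake".
- **BIS-11.** The project timeline lists the measures before treatment as "Brief Addiction Monitor (BAM), Barrett Impulsivity Scale-11 (BIS-11), Posttraumatic Checklist-5 (PCL-5), Beck's Anxiety Inventory".

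After treatment, the timeline lists "BIS-11, Delay Discounting Task, Stop-Signal Task, Emotional Go-NoGo task, Quality of Life Inventory". BDI-II is described among the Visit Two questionnaires ("The BDI-II is a 21-question, multiple-choice self-report questionnaire") but does not appear in the timeline's post-treatment measures.

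Section 7 says Veterans are allocated at random to their individual-therapy provider: two providers deliver MFP and a different one gives supportive therapy. Section 3 gives the size: "This protocol will recruit approximately 35 Veterans".

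**The concern.** Under random assignment, the post-score t-test, the change-score comparison and the baseline-adjusted comparison all estimate the same MFP versus TAU difference. They differ in precision. The t-test leaves any chance imbalance in intake QOLI in the estimate. With two time points, the group interaction is a test on change scores, which fixes the coefficient of the intake score at 1 instead of estimating it. ANCOVA estimates that coefficient.

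Two things are at stake. First, with about 35 Veterans there is little precision to spare. Second, QOLI has two group tests that can disagree on the same data, and the protocol does not say which one counts.

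**Working it through.** **Inputs from the protocol.** About 35 Veterans (section 3); intake QOLI and BDI (sections 3 and 4.a); Visit 2 QOLI (section 4.b and timeline); random assignment to provider, ratio not given (section 7). The protocol gives no SD, effect size, alpha, power or pre-post correlation, so there is no stated figure to reproduce.

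**Assumptions.** Equal SDs before and after treatment and in both groups; pre-post correlation r between 0.3 and 0.7; no other covariates in the model. The interaction is read as group by time, with two time points.

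**Relative variance of the group difference.**
- Post-score t-test: 1
- Group interaction (change score): 1 + 1 − 2r = 2(1 − r)
- ANCOVA on the intake score: 1 − r²

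The saving of ANCOVA against the t-test is r². Against the interaction, the ratio is (1 − r²) / [2(1 − r)] = (1 + r)/2, so the saving is (1 − r)/2.

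| r | t-test | interaction | ANCOVA | saved v t-test | saved v interaction |
|---|---|---|---|---|---|
| 0.3 | 1.00 | 1.40 | 0.91 | 9% | 35% |
| 0.5 | 1.00 | 1.00 | 0.75 | 25% | 25% |
| 0.7 | 1.00 | 0.60 | 0.51 | 49% | 15% |

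Since r² is at least 0 and (1 + r)/2 is at most 1, ANCOVA is never behind either method on this measure. The interaction beats the t-test only when 2(1 − r) < 1, that is, when r > 0.5.

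**What this means at about 35 Veterans.** Power is from the noncentral t, with assumed two-sided alpha 0.05 and an assumed difference of 0.8 SD. Error degrees of freedom are 33 for the t-test and interaction, and 32 for ANCOVA. The 23 v 12 split is what three equally loaded providers would give (35 × 2/3 = 23.3).

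| split | r | t-test | interaction | ANCOVA |
|---|---|---|---|---|
| 18 v 17 | 0.3 | 63.2% | 49.2% | 67.2% |
| 18 v 17 | 0.5 | 63.2% | 63.2% | 75.4% |
| 18 v 17 | 0.7 | 63.2% | 84.2% | 89.5% |
| 23 v 12 | 0.3 | 58.7% | 45.4% | 62.7% |
| 23 v 12 | 0.5 | 58.7% | 58.7% | 71.1% |
| 23 v 12 | 0.7 | 58.7% | 80.4% | 86.2% |

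At 18 v 17, the difference detectable with 80% power is 0.98 SD for the t-test. For ANCOVA it is 0.93, 0.85 and 0.70 SD at r = 0.3, 0.5 and 0.7. The lost degree of freedom is already in these figures.

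**Chance imbalance.** At 18 v 17, the difference between groups in mean intake score has an SD of √(1/18 + 1/17) = 0.34 intake SDs. With equal SDs, the unadjusted t-test carries r times any such imbalance into the QOLI contrast.

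**The case against.** The strongest reply is that baseline is not ignored. The repeated-measures interaction uses intake QOLI and BDI, so a reader who inferred that no group comparison takes account of pre-treatment values would be wrong. What remains is a choice between two accepted uses of baseline. That stands. It leaves open the inefficiency of the change score when r is low or moderate, and the duplicate QOLI test.

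Other parts of the reply also stand:

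- **Size.** A reader might take a quarter as the loss. That figure needs r = 0.5, which the protocol does not give. If PTSD and anxiety scores already explain some of the outcome variance, the added gain from the intake score may be smaller than 1 − r² suggests.
- **Covariates.** The open-ended reference to other symptoms could include intake BDI, and a separate analysis plan might list covariates. However, the protocol itself commits to a t-test, which cannot carry covariates.
- **Groups.** The t-test list does not say who is compared. Drug-free urines and retention as dependent variables suggest treatment groups. The QOLI description in section 4.b, though, states a hypothesis by treatment adherence. If the list means adherence groups, deleting its QOLI test would remove the test of that hypothesis.
- **BIS-11.** A reader might see its missing MFP versus TAU contrast as a gap in the exploratory aim. The protocol does not support that. The aim concerns neurobehavioral function, section 2 separates trait scales from behavioral tasks, and Data Analysis expects no change in trait impulsivity over this period.
- **Other outcomes.** Delay discounting, stop-signal, Go-NoGo and Tower measures are taken only at Visit 2, so no baseline information is lost there.

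**Conclusion.** The point holds for MFP versus TAU on QOLI and depression. QOLI has two overlapping tests without a stated priority, depression has the change-score interaction only, and neither method uses the intake score as a covariate. With random assignment and equal SDs, baseline-adjusted ANCOVA would have 9% to 49% less variance than the t-test and 35% to 15% less than the interaction as r runs from 0.3 to 0.7, apart from one degree of freedom and before the planned covariates. The preference for ANCOVA does not depend on r; the size of the gain does.

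The t-test criticism applies to QOLI alone, since BDI-II and BIS-11 are not in that list. Because comparison by treatment is an exploratory aim, this is a worthwhile improvement rather than a flaw that invalidates the plan.

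**What to change.** - **QOLI.** Make the single MFP versus TAU test an ANCOVA of the Visit 2 score on assigned therapy, adjusting for intake QOLI. It replaces both the MFP versus TAU t-test and the interaction test. The planned PTSD and anxiety covariates can enter the same model.
- **BDI-II.** Use the same model with intake BDI, where the Visit 2 score is collected. First reconcile the Visit Two measure list, which includes BDI-II, with the project timeline, which omits it after treatment.
- **t-test list.** State which groups it compares. Keep any QOLI comparison by adherence as a separate analysis.
- **Pre-post change.** Keep it as description.
- **BIS-11.** If a group contrast is reported, use the same model with the Visit 1 score and label it exploratory.

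The cost is analysis wording only. For QOLI and BIS-11 both scores are already scheduled. For BDI-II it depends on the reconciliation above.

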## **7. Recruitment:**

Recruitment: This project will recruit Veterans enrolled in the Substance Abuse Intensive Outpatient Program (IOP). The IOP includes five different groups over three days of the week for four weeks. Veterans are also randomly assigned to meet with a provider for four weekly individual sessions. Currently, Veterans either meet with one of two providers to complete the Mind Freedom Plan treatment, or they meet with a different provider to receive supportive, unstructured, therapy.

For the study, Veterans will be identified in their medical chart as being enrolled in IOP following the clinic intake and prior to beginning treatment. Research staff will contact Veterans face to face when they present to the SATP clinic to provide information about the study and explore if they are interested in participating. If they express interest, staff will schedule an appointment to meet with the potential participant to introduce the study, review and sign consent, and complete the baseline assessment self-report measure before they begin treatment.

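### Pre-post change in depression and quality of life is labelled an effect of the treatments although every subject attends the same IOP and no arm is untreated; the interaction should read group x time

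*Protocol*

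**What the plan says.** The Data Analysis part of protocol section 4.b plans this for depression and quality of life: "A repeated-measures design will be used to examine the within-subjects effects of the treatments on state depression and quality of life". The sentence goes on: "as well as for a group X treatment interaction effect". It names no time or visit factor. Later in the same paragraph comes "a between-group design comparing the MFP group vs. TAU group", with PTSD, anxiety and other symptom measures as covariates. A list of independent-group tests at the head of the section includes the QOLI score but not the BDI-II.

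The two measurement occasions are as follows. The pre-treatment values are taken from the chart: "results of the Beck Depression Inventory and Quality of Life Inventory administered during the SATP intake" (section 4.a). The post-treatment values come from the second visit: "Subjects will then meet with research staff again approximately one month later following their completion (or potentially incompletion) of the treatment" (section 3).

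On what subjects receive, the timeline table in section 4.b says "Participants engage in either MFP or TAU treatment during their IOP engagement". Section 7 adds "The IOP includes five different groups over three days of the week for four weeks" and, on the individual therapy, "Veterans are also randomly assigned to meet with a provider for four weekly individual sessions".

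**The concern.** A within-subject contrast over about a month estimates everything that changed in that month. All subjects are in the IOP, and the two arms differ only in the four individual sessions. With no untreated or waiting arm, change within subjects cannot be divided between the individual therapy, the group programme, time and any regression to the mean. The protocol nevertheless calls it an effect of the treatments. Section 5 raises the stakes by saying that the study could show a brief cognitive intervention to be effective. A significant pre-post improvement could be reported in that sense when MFP and TAU do not differ at all.

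The second part concerns the interaction. The contrast that bears on MFP against TAU in a two-occasion design is whether change differs by arm. The term as written does not say that.

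**Working it through.** The protocol gives no alpha, SD, correlation or effect size for this analysis, so there is no figure of its own to reproduce.

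**Inputs from the protocol:** about 35 subjects (section 3); two occasions, intake and Visit Two; two active arms. **Assumed:** two-sided alpha 0.05; complete pairs; pre-post correlation r of 0.5 to 0.7; equal SD at both occasions; an arm split of 17/18, or 23/12 because two providers give MFP and one gives supportive therapy.

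**1. The interaction term.** The only groups named are MFP and TAU, which are also the treatments. Coding both factors that way for 35 subjects at 2 visits:

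- intercept, group, treatment, group x treatment: rank 2 of 4 columns, so the interaction cannot be estimated;
- intercept, group, time, group x time: rank 4 of 4, and the interaction is the MFP minus TAU difference in mean change.

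**2. The paired test when the arms do not differ.** Let both arms improve by c SD for any shared reason (a fall on BDI-II, a rise on QOLI). In SD units the difference score has SD = sqrt(2(1 - r)), which is 1.000 at r = 0.5 and 0.775 at r = 0.7. The noncentrality is c x sqrt(35) / sqrt(2(1 - r)) on 34 df. For c = 0.3 this is 0.3 x 5.916 / 1.000 = 1.77, or 0.3 x 5.916 / 0.775 = 2.29.

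| Shared change | P(significant), r = 0.5 | P(significant), r = 0.7 |
|---|---|---|
| 0.2 SD | 21% | 32% |
| 0.3 SD | 41% | 61% |
| 0.5 SD | 82% | 96% |

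In all these cases the group x time null hypothesis is true, so that test rejects 5% of the time.

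**3. What group x time can detect.** The noncentrality is d / (sqrt(2(1 - r)) x sqrt(1/n1 + 1/n2)) on 33 df, where d is the difference in change between arms.

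| Difference in change | Power, 17/18 | Power, 23/12 |
|---|---|---|
| 0.3 SD | 14-20% | 13-18% |
| 0.5 SD | 30-46% | 28-42% |
| 0.8 SD | 63-84% | 59-80% |

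**4. Why ANCOVA is the better form.** Relative to the variance of a single score, the residual variance is 1 for an unadjusted post-treatment comparison, 2(1 - r) for change and 1 - r² for ANCOVA. At r = 0.5 these are 1, 1.00 and 0.75; at r = 0.7 they are 1, 0.60 and 0.51. ANCOVA has the smallest at both ends of the range.

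**5. Whether the post-treatment depression score is collected.** The Visit Two list in section 4.b includes the BDI-II. The timeline table gives the Day 29-35 measures without it and mentions the Beck Depression Inventory there only as a chart-review item. The QOLI is among the Visit Two measures in both places.

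**The case against.** The strongest reply is that the interaction is only loosely labelled. The sentence concerns a repeated-measures design, and the timeline speaks of pre- and post-treatment assessments, so treatment may stand for pre against post. The term would then already be group x time. That is plausible and cannot be excluded. The protocol does not define the term, however, and uses the plural of the same word for the therapies earlier in the sentence. The repair is a relabelling on either reading, and the attribution problem does not depend on it.

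Four stronger readings are tempting, and the document does not support them.

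- *The interaction was put there to safeguard the within-subject interpretation.* The protocol sets the two analyses side by side and says nothing of the kind.
- *The MFP versus TAU contrast is lost.* The same paragraph plans a separate between-group comparison with covariates, and section 7 describes random assignment to providers, so a post-treatment comparison is informative. What stands is that neither that comparison nor the QOLI t-test mentions the intake score, and that the BDI-II is not on the t-test list.
- *BIS-11 change is misattributed too.* The protocol describes it only as exploratory within-subject change and expects none.
- *Intake is a symptom peak, so regression to the mean must be large.* Eligibility sets no BDI or QOLI threshold, and the protocol gives no intake level or retest correlation. Regression to the mean is one possible component of unknown size, which is why the illustration uses a shared change from any cause.

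It is also fair to say that the comparison of modalities belongs to the exploratory aim, and that rewording does not supply an untreated arm.

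**Conclusion.** The point holds as a matter of attribution and wording. Pre-post change in BDI-II and QOLI is change during IOP, and the design does not allow it to be called an effect of either treatment. A shared 0.3 SD improvement would give a significant paired test about 41% to 61% of the time with no MFP-TAU difference. This illustrates the mechanism and does not forecast this study's result: it rests on 35 complete pairs, two-sided 0.05 and r of 0.5 to 0.7, and the size of any shared change is unknown. The 5% for group x time assumes that the shared change really is equal in both arms.

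The interaction label needs correcting to group x time, whether or not that was the intention. Group x time, or ANCOVA, isolates only the difference between MFP and TAU; it does not turn the pooled change into a treatment effect. At this sample size its power is modest for anything short of a large difference, which is a reason to report the estimate with its interval and no reason to fall back on the pooled change.

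**What to change.** In the Data Analysis section, replace the repeated-measures sentence with wording such as: *The effect of MFP relative to TAU on BDI-II and QOLI will be estimated by ANCOVA of the Visit Two score on the intake score with group as factor (or by group x time). The main effect of time will be reported as change during IOP and will not be attributed to either treatment.* State that this replaces the unadjusted QOLI t-test for the MFP versus TAU contrast. The BIS-11 sentence can stand.

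Reconcile the timeline table with the Visit Two list on whether the BDI-II is given at Day 29-35; without it the depression analysis has no post-treatment score.

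The cost is a few lines of text. The intake values are already to be abstracted from the chart, and no new measure is needed beyond those that the Visit Two list already names.

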**Visit One:**

The following self-report measures (questionnaires) will be administered with paper-and-pencil:

*Brief Addiction Monitor (BAM)* – The BAM is a 17-item self-report questionnaire that assesses the recent occurrence and frequency of various substances, including marijuana, cocaine, stimulants, and opiates. It additionally has items for the rater to respond to recent health (excellent, very good, good, fair, poor), and recent engagement in risky situations or treatment. Lastly, it has several items asking about symptoms of substance use disorder, such as cravings and difficulties related to substance use (Cacciola et al., 2013). We hypothesize subjects with more reported substance use and less engagement in treatment resources will have poorer treatment adherence. This measure will take approximately 10 minutes to complete.

*Barratt Impulsiveness Scale (BIS-11)* - The BIS-11 is a reliable and valid self-report measure of attentional, motor, and non-planning impulsivity composed of 30 items rated on a 4 point Likert scale from rarely/never to almost always/always (Patton, Stanford, & Barratt, 1995). We hypothesize subjects with higher impulsivity will be more likely to have poorer treatment adherence. This measure will take approximately 10 minutes to complete.

*PTSD Checklist 5* - This is a VA-distributed measure of 20 PTSD-related symptoms (each scored from 0-4) that align with DSM-5 PTSD criteria. It is administered in addition to the SCID itself in order to provide a continuous variable of PTSD symptom severity (Bovin et al., 2016). This measure is being used to account for potential confounding symptomology that may lead to treatment adherence issues. This measure will take approximately 10 minutes to complete.

*Beck Anxiety Inventory* - This is a tally of the subject's self-reported experience of 21 different anxiety-related symptoms in the past week-including the day of testing, where each item is rated on a scale from 0-3 (A. T. Beck, Epstein, Brown, & Steer, 1988). This measure is being used to

account for potential confounding symptomology that may lead to treatment adherence issues. This measure will take approximately 10 minutes to complete.

Visit Two:

The following self-report measures (questionnaires) will be administered with paper-and-pencil:

*Barratt Impulsiveness Scale (BIS-11)* – See above for description

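### Substance use symptomology is named a primary outcome of the MFP versus TAU comparison, but the only instrument that measures it, the BAM, is scheduled only before treatment

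*Protocol*

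**What the plan says.** The last comparison in the Data Analysis section is a between-group design "comparing the MFP group vs. TAU group for substance use primary outcomes of symptomology", and also on task measures of impulsivity and problem solving. The sentence ties symptomology to no instrument.

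Section 4.b describes the BAM under Visit One: "it has several items asking about symptoms of substance use disorder, such as cravings and difficulties related to substance use". It also covers recent use of individual substances. The hypothesis attached to it concerns prediction: "We hypothesize subjects with more reported substance use and less engagement in treatment resources will have poorer treatment adherence".

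The project timeline lists these measures for Day -7 to Day -1: "Brief Addiction Monitor (BAM), Barrett Impulsivity Scale-11 (BIS-11), Posttraumatic Checklist-5 (PCL-5), Beck's Anxiety Inventory". For Day 29 to Day 35 it lists: "BIS-11, Delay Discounting Task, Stop-Signal Task, Emotional Go-NoGo task, Quality of Life Inventory". The Day 120 row is a chart review only.

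Section 1 places the comparison of treatment modalities under an Exploratory Aim about neurobehavioral function. The outcomes of Aim 1 are toxicology results, missed appointments, early drop-out and recidivism.

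**The concern.** An outcome that compares two treatments must be measured after treatment has begun to act. Here the comparison names substance use symptoms as primary, while the schedule collects the matching scale only in the week before the programme starts. Taken literally, the analysis would either compare the groups on a pre-treatment score, which can show only baseline imbalance, or have nothing to compare.

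A statistical analysis plan cannot repair this. It can define a score or a model, but it cannot supply an assessment that the visit schedule does not contain. Symptoms and craving not recorded at Day 29 to 35 cannot be recovered later. The subject matters to the sponsor's case as well: Section 2 asks whether structured therapy may lower substance use, and Section 5 says the study could show that the intervention is effective in this population.

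**Working it through.** **Step 1: where is each candidate measure taken?** The plan gives no figure for this point, so the check sets the named outcome against every list of measures (Section 4.b, the project timeline, the chart reviews in Sections 3 and 4.a, and the Data Analysis list).

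| Candidate for substance use symptomology | Before treatment | Day 29–35 | Day 120 | Fits the words? |
|---|---|---|---|---|
| BAM (symptoms, craving, self-reported use) | yes | no | no | yes |
| UDS / breathalyzer from the chart | – | yes | yes | measures use, not symptoms |
| BDI-II | intake score, from chart | yes | see note | depression, not substance use |
| PCL-5, Beck Anxiety Inventory | yes | no | no | covariates in Data Analysis |

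Note: Sections 3 and 4.a say the 90-day review collects the same chart information where it exists. The Day 120 timeline row names only treatment re-entry and toxicology.

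The Day 29–35 timeline row alone would be weak evidence, because it also omits the BDI-II and the Tower Test, both of which Section 4.b lists at Visit Two. The BAM, however, is missing from the fuller Visit Two list in Section 4.b as well, and from both chart reviews. Scheduled BAM assessments after treatment: 0.

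**Step 2: do the other readings work?**
- Toxicology: the proportion of drug-free urines is already the first dependent variable in the Data Analysis list, and a urine result is not a symptom.
- BDI-II: the protocol describes it as used "for the purposes of measuring reported symptoms of depression", and depression has its own repeated-measures sentence.
- PTSD and anxiety scales: these are adjustment variables, and they too are taken only before treatment.

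**Step 3: is there a policy of taking trait-like scales only once?** No. The BIS-11 is repeated at Visit Two although the Data Analysis section does not expect it to change.

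**Step 4: would the BAM fit into Visit Two?** Minutes from Section 4.b: BIS-11 10 + QOLI 10 + BDI-II 10 + Tower Test 10 + delay discounting 15 + stop-signal 12 + Emotional Go-NoGo 14 = 81. Adding the BAM: 81 + 10 = 91. Section 4.a gives about 2 hours for this visit; Subject Compensation in Section 5 gives 90 minutes. The sum leaves out instructions and changeovers.

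**Step 5: what might baseline adjustment gain? (illustration only)** The protocol states no alpha, power, allocation ratio or correlation. Assume a 17:18 split of 35, two-sided alpha 0.05, 80% power and full attendance at Visit Two. The detectable standardized difference for a two-sample t-test is then d = 0.98. Adjusting for a baseline score correlated r with the outcome multiplies this by about √(1 − r²):
- r = 0.3: 0.98 × 0.954 = 0.93
- r = 0.6: 0.98 × 0.800 = 0.78
- r = 0.7: 0.98 × 0.714 = 0.70

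An even split is itself uncertain, because Section 7 has two providers delivering MFP and one delivering supportive therapy. A 23:12 split gives 1.03 unadjusted and 0.82 at r = 0.6. With 14:14 completing, the values are 1.10 and 0.88.

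**The case against.** The best defence is that the protocol never links symptomology to the BAM. The only hypothesis stated for the BAM is that it predicts adherence, which needs a baseline score and nothing more, and the BAM is not among the numbered dependent variables. Elsewhere the protocol uses symptomology and symptomatology mainly for PTSD, anxiety and mood. On this view the sentence is loosely worded and no assessment was forgotten. This stands in part: the document does not say which of the two happened, so a change of wording has to be offered as an alternative to a new assessment. It does not remove the mismatch, because the words substance use rule out the mood and anxiety scales, and no other instrument fits.

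A reader might go further and infer that the study cannot estimate any effect on substance use. The documents do not support that. UDS and breathalyzer results are extracted per participant after Visit Two and again 90 days later, and the proportion of drug-free urines is a listed outcome. These results do depend on what the clinic collected, and for the post-treatment period they are taken only where they exist.

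A reader might also infer that the study's main question fails. It does not. Aim 1 uses outcomes that are all scheduled, and the group comparison is exploratory, even though the analysis text calls these outcomes primary.

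**Conclusion.** The point holds in a limited form. An outcome called primary for the MFP versus TAU comparison has no post-treatment measurement: zero scheduled BAM assessments after baseline, for about 35 participants. What is missing is post-treatment symptoms, craving and self-reported use; toxicology is available from the chart. The conclusion rests on reading symptomology as symptoms of substance use disorder, the only reading that fits the sentence. If another meaning was intended, the text still needs changing.

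It does not depend on the power figures. The fall from 0.98 to between 0.93 and 0.70, for r from 0.3 to 0.7 at a 17:18 split, only shows what a paired baseline could offer under assumptions the protocol does not state. Because the comparison is exploratory, this is a cheap improvement worth making and not a flaw that undermines the study.

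**What to change.** Add the BAM to the Visit Two measures in Section 4.b and to the Day 29–35 row of the timeline. In Data Analysis, name the Visit Two BAM as the symptomology outcome, and compare MFP with TAU on it with the Visit One BAM as covariate. If the sponsor meant toxicology, replace symptomology with the UDS/breathalyzer outcome instead; no new data are then needed. In either case, reconcile the word primary in Data Analysis with the exploratory label in Section 1.

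The cost of repeating the BAM is one 17-item questionnaire of about 10 minutes at an existing visit, plus a short amendment. Listed tasks would total 91 minutes, so the two stated lengths of the second visit (about 2 hours in Section 4.a, 90 minutes under Subject Compensation) should be brought into line at the same time. Participants who have already passed Visit Two when the amendment takes effect would have no follow-up BAM, so the change is worth most if made early.
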